### 1.2. KPT-9274

KPT-9274 is a first-in-class orally bioavailable small molecule that is a non-competitive dual modulator of p21 protein (Cdc42/Rac)-activated kinase 4 (PAK4) and nicotinamide phosphoribosyltransferase/PBEF/visfatin (NAMPT). Co-inhibition of these targets leads to synergistic anti-tumor effects through energy depletion, inhibition of deoxyribonucleic acid (DNA) repair, cell cycle arrest, inhibition of proliferation, and ultimately apoptosis. Normal cells are more resistant to inhibition by KPT-9274 due in part to their relative genomic stability and lower metabolic rates.

KPT-9274 demonstrated potent anti-proliferative activity against cancer cell lines (solid tumor cells MTT median IC50: 135 nM, range 0.007 to >10 μM; hematological cancer cells MTT median IC50: 40 nM, range 0.003 to >10 μM) with minimal toxicity to normal cells (median MTT IC50: ~0.9 μM, range 0.033 to >10 μM). In mouse xenograft studies, KPT-9274 (oral 50-200 mg/kg twice daily for 5 days/week) was well tolerated and resulted in a marked reduction in tumor size across a variety of tumors, including colon, pancreatic, lung, multiple myeloma, leukemia, and lymphoma. In approximately half of the tumor types studied, complete elimination of tumors in as short as 3 weeks was observed with no regrowth after cessation of treatment (up to 3 weeks). In other cell types tumor growth inhibition was observed. KPT-9274 was able to control systemic acute B lymphoblastic leukemia (B-ALL) and acute myeloid leukemia (AML) tumor growth and significantly extended overall survival. Moreover, KPT-9274 has shown preliminary efficacy in companion dogs with spontaneous advanced lymphomas and multiple myeloma (MM).

Unlike the Pan-PAK inhibitor (PF-3758309), or the NAMPT inhibitors (APO866 and GMX1777/GMX1778) that advanced to human clinical trials, the dual NAMPT/PAK inhibitor KPT-9274 demonstrates consistent pharmacokinetic (PK) properties (e.g., oral absorption), exhibits minimal brain penetration, and does not inhibit any of the cytochrome P450 (CYP450) enzymes. The nonclinical toxicity profile of KPT-9274 recapitulates the expected class level gastrointestinal (GI) and hematopoietic toxicities but not the retinal and cardiac effects observed preclinically with some NAMPT inhibitors. The lack of retinal and cardiac effects of KPT-9274 may be attributed to its minimal permeability and decreased potency compared to other NAMPT inhibitors. Furthermore, no orally available PAK4 selective inhibitors have been developed to date. Thus, KPT-9274 captures many of the favorable therapeutic aspects of targeting both NAMPT and PAK4 with the potential for reduced adverse effects.

Preliminary two-week non-good laboratory practices (GLP) toxicology studies in rats and dogs suggest that KPT-9274 has an acceptable tolerability profile. The dog has been identified as the most sensitive species for KPT-9274 GI toxicity, with rats also showing GI toxicity at significantly higher doses. The primary KPT-9274 toxicity that has been observed in dogs is gastrointestinal hemorrhages in the small intestine, colon, and rectum. Other target organ effects include hypocellularity in the bone marrow and lymphoid depletion in the lymphoid tissues.

Nicotinamide adenine dinucleotide (NAD) regeneration pathways can bypass NAMPT inhibition by utilizing niacin (vitamin B3/nicotinic acid) through nicotinate phosphoribosyltransferase (NAPRT1). Supplemented niacin can alleviate adverse events due to NAMPT inhibition when tissues express NAPRT1. However, NAPRT1 is frequently repressed in tumors (through epigenetic modulation or isocitrate dehydrogenase 1 (NADP+), soluble [IDH1] mutation) while remaining intact in surrounding normal tissue potentially increasing therapeutic index in the presence of niacin. Additional exploratory studies and data from 4-week GLP studies indicate that co-administration of niacin can increase tolerability of KPT-9274 in dogs. These data demonstrate that a dose of KPT-9274 previously shown to have an adverse toxicologic profile was tolerable and had minimal GI macroscopic findings. For this reason, co-administration of KPT-9274 with niacin in patients with or without NAPRT1 or IDH1 mutation in their tumors is planned.

KPT-9274 demonstrated anti-tumor activity in dogs with spontaneous advanced lymphomas and multiple myeloma. Patient dog #1 was given 4 doses of 2 mg/kg KPT-9274 and had progressive disease after 1 week. This patient dog was given 25 mg/kg doxorubicin (Adriamycin) on Day 8 (~24 hours post-final KPT-9274 dose). The bulk disease responded shortly thereafter with a partial response (PR) at the end of week 2 that transitioned into a complete response (CR). As of October 2015, the patient dog remains in complete remission for >4 months off all therapy with no AEs reported to date. A T-cell lymphoma dog experienced a ~1 week PR at 2 mg/kg of KPT-9274 every other day (QOD)  $\times$  3 but subsequently progressed. A patient dog with refractory multiple myeloma (4 lines of previous therapy) treated with 3 mg/kg of KPT-9274 QOD  $\times$  3 plus prednisone had a PR with decreases in globulins and resolution of anemia and thrombocytopenia for ~5 weeks, but progressed during Week 6. Two additional B-cell lymphoma dogs did not respond to 2 mg/kg or 3 mg/kg of KPT-9274 QOD  $\times$  3 in which one dog (2 mg/kg dose) had low drug levels in the plasma. These preliminary results suggest that KPT-9274 show anti-tumor activity both as a single agent and in combination with DNA damaging agents (DDA) with minimal or no side effects observed. Dose escalation evaluation in patient dogs with lymphoma and solid tumors is on-going.

KPT-9274 has clear preclinical anti-tumor activity (*in vitro* and *in vivo*) as well as an encouraging safety profile (compared to previously described Pan-PAK and NAMPT inhibitors) making it an attractive novel drug candidate. Since both solid tumor and hematologic malignancies were seen to be susceptible to single-agent cytotoxicity with KPT-9274, development is planned in both areas.

### 1.2.1. Potential Risks

In the completed study, KCP-9274-901, 50 patients had received KPT-9274 alone or with niacin ER, and an additional 10 patients received KPT-9274 in combination with nivolumab. The most common AEs occurring across all patients include the following: anemia (81.7%, 49/60), fatigue (45.0%, 27/60), arthralgia (40.0%, 24/60), nausea (40%, 24/60), dyspnea (33.3%, 20/60), diarrhea (31.7%, 19/60), vomiting (26.7%, 16/60), myalgia (23.3%, 14/60), decreased appetite (21.7%, 13/60), flushing (21.7%, 13/60), and abdominal pain (20.0%, 12/60). The following events were identified as potential risks of KPT-9274: anemia, fatigue, arthralgia and myalgia, and nausea. AEs were largely dose dependent and increased with higher doses of KPT-9274. A total of 3 DLTs were reported during the study, one at the 40 mg QODx3 dose and two at the 80 mg + niacin

QODx3 dose. Maximum tolerable dose was not reached in either Part A (KPT-9274 monotherapy) or B (KPT-9274 with niacin ER).

### **1.2.2. Reproductive Risks of KPT-9274**

It is unknown whether KPT-9274 might have reproductive toxicity in humans; therefore, all patients in this study must agree to use effective contraception (see Prevention of Pregnancy, Section 5.7.2.2) during the study, and for 3 months after their last dose of KPT-9274.

## **1.3. Study Rationale**

KPT-9274 is a first-in-class orally bioavailable, non-competitive, small molecule, dual modulator of PAK4 and NAMPT. NAMPT is the rate-limiting enzyme in the metabolic scavenging pathway that utilizes nicotinamide to replenish nicotinamide adenine dinucleotide (NAD), an essential metabolic cofactor and second messenger.

Hematologic and solid tumor cells are susceptible to single-agent cytotoxicity by KPT-9274 as they become dependent on both the PAK4 and NAMPT pathways. KPT-9274 demonstrated potent anti-proliferative activity against cancer cell lines with minimal toxicity to normal cells. In mouse xenograft studies, KPT-9274 was well tolerated and resulted in a marked reduction/elimination of tumors, tumor growth inhibition or disease control across a variety of tumors, including colon, pancreatic, lung, sarcoma, multiple myeloma, leukemia, and lymphoma. In approximately half of the tumor types studied, complete elimination of tumors in as short as 3 weeks was observed with no regrowth after cessation of treatment (for up to 3 additional weeks). Moreover, KPT-9274 has shown preliminary efficacy in companion dogs with spontaneous advanced lymphomas and multiple myeloma.

In AML, pre-clinical studies have shown increased dependency of AML cells on NAMPT, and in the clinical setting, higher NAMPT expression is associated with decreased overall survival. In an AML model, KPT-9274 depleted NAD+, resulting in loss of mitochondrial respiration and glycolysis and apoptosis, regardless of mutational/genomic profiles. Furthermore, emerging data suggests that targeting NAMPT can specifically eradicate the relapsed/refractory leukemia stem cell population, which has previously not had any promising therapeutic opportunities (Jones et al, Cell Stem Cell 2020 Nov 5;27(5):748-764).

### **1.3.1. Rationale for the Starting KPT-9274 Dose**

In the first-in-human solid tumor Phase 1 study, patients received oral KPT-9274 three times a week every other day (Days 1, 3, 5, 8, 10, 12, 15, 17, 19, 22, 24, and 26) during each 28-day cycle. A starting dose of 10 mg KPT-9274 was selected and escalated to 40 mg. The study was stopped but the MTD was not reached, and there was only one DLT in a patient who received KPT-9274 alone (anemia). Based on this experience, in the current study patients will receive oral KPT-9274 three times a week every other day (Days 1, 3, 5, 8, 10, 12, 15, 17, 19, 22, 24, and 26) during each 28-day cycle, and the first dose cohort will be 30 mg.

## **1.4. Objectives**

### **1.4.1. Primary Objective**

- To assess the maximum tolerated dose (MTD)

### **1.4.2. Secondary Objective**

- To establish a recommended phase 2 dose (RP2D)

***Dose Expansion (if conducted)***

- To determine preliminary evidence of efficacy of KPT-9274 at the RP2D

## **1.5. Endpoints**

### **1.5.1. Safety Endpoints**

- The occurrence of dose limiting toxicities (DLTs) and the occurrence, nature and severity of adverse events (AEs)

### **2.2.2. Efficacy Endpoints (if dose expansion is conducted)**

- Primary Endpoint: Overall response rate (ORR)
- Secondary Endpoint: Duration of response (DOR), progression-free survival (PFS), overall survival (OS)

Disease response will be evaluated according to the European Leukemia Network (AML) ([Appendix 2](#)) and will include the following:

- **Overall response rate (ORR):** complete remission (CR), complete remission with incomplete hematologic recovery (CRi), morphologic leukemia-free state (MLFS), partial remission (PR).
- **Duration of response (DOR):** the duration of time from first meeting CR, PR, MLFS, CRi, measurement criteria (whichever occurs first) until the first date that progressive disease (PD) is objectively documented.
- **Progression-free survival (PFS):** the duration of time from date of first study treatment until the first date that disease progression is objectively documented or death due to any cause.
- **Overall survival (OS):** the duration of time from date of first study treatment until death from any cause.

## 2. INVESTIGATIONAL PLAN

### 2.1. Overall Study Design and Plan

This is a first-in-disease, single-center, open-label dose escalation clinical study to assess preliminary safety, tolerability, and efficacy of KPT-9274, a dual inhibitor of PAK4 and NAMPT, in patients with relapsed or refractory AML for whom all standard therapeutic options considered useful by the investigator have been exhausted.

During dose escalation, patients will receive oral KPT-9274 three times a week every other day (Days 1, 3, 5, 8, 10, 12, 15, 17, 19, 22, 24, and 26) during each 28-day cycle, and the first dose cohort will be 30 mg. Subsequent dose escalation cohorts, as well as a de-escalation cohort, will be administered per the table below. Dose escalation will continue until the MTD is determined. The MTD is defined as the highest dose at which  $\leq 1$  patient experiences a DLT in Cycle 1. A RP2D equal to or less than the MTD will be declared and used for the Dose Expansion Phase, if conducted.

Patients must complete a minimum of 1 cycle of treatment, defined as receiving  $\geq 75\%$  of KPT-9274 doses during Cycle 1 (e.g.,  $\geq 9$  of 12 doses in the 3 doses/week schedule), or have a DLT within the first cycle of treatment to be evaluable for dose escalation decisions. The cycle length is 28 days the DLT period is the first 28 days of cycle 1. Dose escalation decisions will occur when a cohort of patients has met these criteria.

After the RP2D is determined, a dose expansion phase, of up to 10 additional patients, might be conducted, in which a preliminary determination of efficacy will be conducted, using the ELN criteria (Appendix 2). After the RP2D has been established, subjects at lower dose Cohorts may have the option to change dose to the RP2D, per investigator discretion.

Screening will be performed within 30 or 14 days prior to the start of therapy (i.e., Day -30 to Day -1, or Day -14 to Day -1), as summarized in Table 1. The Follow-up period includes the EOT visit, the Safety Follow-up visit, and Durability of Response and Survival Follow-up; see Table 3 for assessments to be completed during the Follow-up period.

The number of patients required for completion of study enrollment cannot be defined *a priori* since this depends on the number of patients needed for the dose escalation; but the maximum number of patients from the escalation and expansion cohorts will be 40.

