***KPT-9274 Dose Escalation Levels***

Cohort	KPT-9274
	Days 1, 3, 5, 8, 10, 12, 15, 17, 19, 22, 24, 26 in a 28-day cycle
0 (de-escalation, if needed)	20 mg
1 (starting cohort)	30 mg
2	40 mg
3	60 mg
4	80 mg
5	100 mg

*\*after the MTD has been established, subjects at lower dose cohorts may have the option to change dose to the MTD, per investigator discretion*

Three patients will be enrolled in each cohort; if 1 of the first 3 patients in a cohort experiences a DLT, the number of patients in that cohort will be expanded to 6 patients. A maximum of 6 patients will be enrolled per cohort. The MTD is defined as the highest dose at which  $\leq 1$  patient out of a maximum potential cohort of 6 experiences a DLT.

A DLT will be defined as an AE or abnormal laboratory value that occurs within the first 28 days of treatment with KPT-9274, except for those that are clearly and incontrovertibly due to underlying disease, disease progression, or extraneous causes, and meets any of the criteria for defining dose-limiting toxicities as described in the table below. CTCAE, Version 5.0 will be used for grading. In addition,  $> 3$  missed (consecutive or nonconsecutive) doses of KPT-9274 in the first 28 days due to a drug related toxicity will be considered a DLT.

Other events may occur which do not meet the definition of a DLT but are of concern to the Investigators may be considered DLTs.

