**DOSE EXPANSION PHASE**

After completion of the Dose Escalation, Dose Expansion in up to 10 additional patients may be conducted to further explore safety, tolerability and preliminary evidence of anti-tumor activity of the RP2D of KPT-9274.

After the MTD has been established, subjects at lower dose cohorts may have the option to change dose to the MTD, per investigator discretion.

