***Statistical Methods:******Sample size justification***

The sample size for the Dose Escalation Phase is based on a standard 3+3 design for the purpose of determining the RP2D and MTD. For the Dose Expansion Phase, up to 10 additional patients may be enrolled at the RP2D for KPT-9274.

**Table 1** Schedule of Assessments: Screening and Cycle 1

	Screening		Cycle 1									
			Week 1			Week 2		Week 3		Week 4		
	Day -30 to Day -1	Day -14 to Day -1	Day 1	Day 2	Dosing Days 3 & 5	Day 8	Dosing Days 10 & 12	Day 15	Dosing Days 17 & 19	Day 22	Dosing Days 24 & 26	Day 28
Window for Assessments (days)	-	-	+/- 1		-	+/- 1	-	+/- 1	-	+/- 1		+/- 3
Visit Type	Clinic	Clinic	Clinic			Clinic		Clinic		Clinic		Clinic
Activity/Assessment												
Informed consent 	X											
Inclusion/exclusion criteria		X										
Patient History												
Demographics	X											
Medical history 	X											
Clinical Assessments												
Patient height	X											
Patient weight	X		X									
Vital Signs (BP, pulse, temp) 	X		X			X		X		X		
Complete physical exam	X											
Symptom-directed physical exam			X			X		X		X		
12-lead ECG 	X 		X 									
ECOG 	X		X									
TLS Monitoring 			X	X								
Clinical Labs												
CBC with differential 		X	X			X		X		X		
Complete metabolic panel 		X	X			X		X		X		
Serum hCG pregnancy test 		X										
Bone marrow aspirate and biopsy 	X					X						X
Dosing of KPT 9274			X		X	X	X	X	X	X	X	
Serious Adverse Events	Continuous (during screening, only SAEs related to study procedures)											
Adverse Events												Continuous
Concomitant Medications												Continuous

Abbreviations: AE = adverse event; CBC = complete blood count; D = Day; ECG = electrocardiogram; ECOG = Eastern Cooperative Oncology Group; EoT = End of Treatment

Historical records related to screening procedures are permitted per Investigator discretion. Sites should adhere to the 28-day cycle.

[name]  
IRB # 20-2350

KPT-9274

- 1 Prior to any study-specific measure.
- 2 A complete medical history will be obtained from each patient. Medical history will include baseline symptoms of the disease under study as well as a detailed history of prior therapies for the patient's AML.
- 3 Vital signs: blood pressure, pulse and body temperature; see Section [6.4.1.2](#) for a detailed description of vital sign assessments.

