- 4 12-Lead ECG to be completed at Screening (Day -30 to Day -1) and C1D1 (pre-dose and 4 hours post-dose (+/- 30 minutes)).
- 5 Complete metabolic panel (CMP) consists of sodium, potassium, chloride, carbon dioxide, glucose, blood urea nitrogen, creatinine, magnesium, phosphorous, uric acid, alkaline phosphatase, alanine aminotransferase, aspartate aminotransferase, bilirubin, protein, albumin and lactate dehydrogenase
- 6 The following procedures must be performed at Screening and pre-dose on C1D1 (and as shown in Table 1, 2, and 3): ECOG performance assessment (Day -30 to Day -1), CBC with differential (Day -14 to Day -1), Complete Metabolic Panel (Day -14 to Day -1).
- 7 For females of childbearing potential, negative serum hCG pregnancy test must be performed  $\leq$  3 days of C1D1 and the EoT Visit. Repeat testing during the study as clinically appropriate.
- 8 Bone marrow biopsies and aspirates will be taken within 30 days prior to first dose (baseline).
- 9 BM - day 28 +/- 3 days; at conclusion of each cycle until the subject has achieved a MLFS, CRi or CR, or per investigator discretion
- 10 TLS Monitoring is defined as "Tumor lysis syndrome monitoring," and occurs on day 1, 8 hours (+/- 2 hours) after the first dose, and on day 2, 24 hours (+/- 4 hours) after the first dose. Labs include potassium, uric acid, phosphorus, calcium, and serum creatinine. TLS labs must be collected at CU Anschutz.

**Table 2** Schedule of Assessments: Cycles 2 and Beyond

	Cycle 2					Cycle 3 and Beyond				
	Week 1-2		Week 3-4			Week 1-2		Week 3-4		
	Day 1	Dosing Days 3,5,8,10,12	Day 15	Dosing Days 17,19,22, 24,26	Day 28	Day 1	Dosing Days 3,5,8,10,12	Day 15	Dosing Days 17,19,22, 24,26	Day 28
Window for Assessments (days)	+/- 1		+/- 1		+/- 3	+/- 1				+/- 3
Visit Type	Clinic		Clinic		Clinic	Clinic				Clinic
Activity/Assessment										
Clinical Assessments										
Patient weight	X		X			X				
Vital Signs (BP, pulse, temp) 	X		X			X				
Symptom-directed physical exam	X		X			X				
ECOG	X					X				
Clinical Labs										
CBC with differential	X		X			X				
Complete metabolic panel 	X		X			X				
Bone marrow biopsy					X 					X 
Dosing of KPT 9274 at Home		X		X			X	X	X	
Adverse events	Continuous				Continuous					
Concomitant medications	Continuous				Continuous					

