### 5.2.6. Dose Escalation Guidelines

#### 5.2.6.1. Dose Escalation Procedures

For the purposes of dose escalation decisions, a standard 3+3 dose escalation design will be used.

The initial cohort, Cohort 1, will consist of 3 enrolled patients who will be treated at 30 mg. If these patients do not experience a DLT during Cycle 1, the KPT-9274 dose will be escalated to 40 mg for another group of 3 patients (Cohort 2). If the MTD is exceeded at cohort 1, de-escalation to cohort 0 (20 mg) will occur. If the MTD is not exceeded in cohort 1, dose escalation will continue based on a standard 3+3 design at the dose levels specified in

Table 8.

A RP2D equal to or less than the MTD will be declared at the conclusion of the dose escalation, and potentially used for the Dose Expansion Phase. The RP2D will be based on an evaluation of any and all pharmacokinetic, pharmacodynamic and safety data, including an evaluation of SAEs that occur after the end of the DLT window to ensure the tolerability of the RP2D. The MTD is defined as the highest dose at which  $\leq 1$  patient experiences a DLT in Cycle 1.

Patients must complete a minimum of 1 cycle of treatment, defined as receiving  $\geq 75\%$  of KPT-9274 doses during Cycle 1 (e.g.,  $\geq 9$  of 12 doses in the 3 doses/week schedule), or have a DLT within the first cycle of treatment to be evaluable for dose escalation decisions. Dose escalation decisions will occur when the cohort of patients has met these criteria.

Dose escalation will be conducted as follows:

- If 0 of 3 patients experiences a DLT, escalate to next higher dose cohort.

- If 1 of 3 patients experiences a DLT, that cohort will be expanded to 6 patients. If 1 of 6 patients experiences a DLT, escalate to the next higher dose cohort;
- If  $\geq 2$  of 3 or  $\geq 2$  of 6 patients experience a DLT, MTD is exceeded. If the MTD is exceeded, the patients will be de-escalated to the next lower dose level (the MTD).

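### After a dose increase to the MTD or RP2D, normally possible only from Cycle 3, blood tests are scheduled on Day 1 of each cycle only, and the ITT wording credits earlier lower-dose time to the RP2D

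*Combined protocol and SAP*

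**What the plan says.** **The option.** Section 2.1 provides that "subjects at lower dose Cohorts may have the option to change dose to the RP2D, per investigator discretion". The synopsis words it for the MTD, both under the dose-level table and under the expansion phase: "subjects at lower dose cohorts may have the option to change dose to the MTD, per investigator discretion". No section names a day in the cycle for the change, restarts the Cycle 1 assessments, or adds laboratory tests.

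**The schedules.** Table 1 ("Schedule of Assessments: Screening and Cycle 1") and Table 2 ("Schedule of Assessments: Cycles 2 and Beyond") are indexed by cycle number, not by time at the current dose. From Cycle 3, Day 15 falls in the row "Dosing of KPT 9274 at Home", and the only clinic visit other than Day 1 is Day 28, for the marrow. Section 6.4.2.1 lets the investigator order tests more often but does not require it.

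**When the option opens.** Escalation waits for each cohort's 28-day window ("If 0 of 3 patients experiences a DLT, escalate to next higher dose cohort"), and "A RP2D equal to or less than the MTD will be declared at the conclusion of the dose escalation".

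**The analysis.** Section 8.3.1 defines the efficacy (ITT) population as anyone who has taken even a single dose at the level selected for expansion. Section 8.1 adds escalation patients treated at that level to the expansion assessments. Section 8.5 starts PFS and OS at the first dose of study treatment, whatever its level.

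**The concern.** Weekly blood tests in Cycle 1 reflect first exposure to a dose. Thinning them to one draw per cycle from Cycle 3 suits a patient who is stable at a constant dose. The option to change up takes effect in just that thin part of the schedule, so a site that follows the plan exactly raises the dose with less laboratory follow-up than a first dose at that level receives.

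The protocol gives reasons to care. Section 1.2.1 describes adverse events as mainly dose dependent, with anemia in 49 of 60 patients (81.7%). Section 1.3.1 reports escalation of the drug alone only to 40 mg, and the 80 mg experience in Section 1.2.1 was with niacin, which Section 5.7.3 prohibits here. An increase to 60, 80 or 100 mg therefore goes beyond the reported monotherapy range. Changes in chemistry, such as transaminases or electrolytes, would be found early only if the investigator chose to look.

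The second stake is interpretation. If changed patients count in the RP2D efficacy population, time survived without progression at a lower dose, and possibly a response reached there, is reported as RP2D experience.

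**Working it through.** The plan states no figure on this point, so the check is a count from its tables.

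**Inputs**
- Scheduled CBC and chemistry: Cycle 1 Days 1, 8, 15, 22 (Table 1); Cycle 2 Days 1, 15; Cycle 3 onward Day 1 only (Table 2). The window and visit-type rows of Table 2 also leave Day 15 empty from Cycle 3, so this does not look like a broken table.
- Dosing days: 1, 3, 5, 8, 10, 12, 15, 17, 19, 22, 24, 26 (Section 5.2.3).
- Cycle and DLT window: 28 days (Section 2.1).

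**Step 1: earliest change.** Take the last patient of a lower cohort, with no accrual gap or cycle delay. Own window 28 days + next cohort's window 28 days = 56, so Day 57, which is Cycle 3 Day 1. That applies only to 80 to 100 mg, since no cohort above 100 mg has to open. For a lower MTD, the cohort above it must also open and exceed the MTD.

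| Change | Ratio | Earliest |
|---|---|---|
| 80 to 100 mg | 100/80 = 1.25 | Day 57 (Cycle 3 Day 1) |
| 30 to 40, 40 to 60, 60 to 80 mg | 1.33, 1.50, 1.33 | mid-Cycle 3 after early DLTs, or Day 85 (Cycle 4 Day 1) |
| 60 to 100 mg | 100/60 = 1.67 | Day 85 (Cycle 4 Day 1) |
| 30 to 60, 40 to 80 mg | 2.0, 2.0 | mid-Cycle 4, or Day 113 (Cycle 5 Day 1) |

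Every route lands in Cycle 3 or later. The Cycle 2 Day 15 draw could help only if that patient's own cycles had been delayed.

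**Step 2: draws after the change.** For a change on cycle day d in Cycle 3 or later, the next scheduled draw is on day 30 - d at the new dose, then every 28 days.

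| | Start at the dose | Change on Day 1 | Change mid-cycle |
|---|---|---|---|
| Draw on the first day | yes | yes | none scheduled |
| Later draws through Day 28 | 3 (Days 8, 15, 22) | 0 | 1 |
| Next draw | Day 8 | Day 29 (+/-1) | Day 27 (d = 3), 15 (d = 15), 4 (d = 26) |
| Later draws through Day 56 | 5 (adds Days 29, 43) | 1 (Day 29) | 2 |
| Doses taken before the next draw | 3 | 12 | 11 (d = 3) down to 1 (d = 26) |

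The Day 28 cut-off matters: counting the Day 29 draw for both groups gives 4 against 1. For chemistry, starters also have tumor lysis panels at about 8 and 24 hours, which are not repeated at a dose change.

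**Step 3: analysis time.** Section 4.2 removes a patient from treatment at progression, so anyone who changes on Day 57 or later has already gone 56 days or more without progression. Section 8.3.1 as worded includes a patient who changes to the RP2D; Section 8.5 starts that patient's PFS and OS clocks on Day 1. Nothing in Section 8.5 excludes from ORR a response reached before the change.

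**The case against.** The strongest case is that the protocol leaves this to clinical judgement. The investigator who decides on the change can order tests, adverse events are collected continuously, and Section 9.8.2 has each patient's outcome discussed at regular meetings. The changed patient is not drug-naive: there are at least 56 days of prior exposure, and the new dose was cleared with at most one DLT. Patients not yet in MLFS, CRi or CR have a Day 28 (+/-3) marrow, and the ELN categories of CR, CRi and PR use neutrophils and platelets, so counts near Day 28 are likely. With residual AML, Table 7 allows no dose adjustment for hematologic toxicity, so an extra CBC would not alter dosing. The common events in Section 1.2.1 are mostly symptoms, with no liver or electrolyte signal.

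Most of that stands and limits the weight of the point. It does not close the gap. Permission is not a schedule, and the plan did not rely on discretion in Cycle 1. The Day 28 marrow comes late, does not call for chemistry, and may be absent in patients already in remission. For those patients Table 7 allows a hold for cytopenia lasting more than two weeks within a cycle, which one Day 1 count cannot show. A cleared dose may also rest on few patients: with 0 DLTs in 3, the one-sided 95% upper bound on the DLT rate is 1 - 0.05^(1/3) = 63%.

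Three stronger readings are tempting and not supported. A reader might infer that a changed patient goes a month with no blood test; a Day 1 change has a draw that day, and more may be ordered. A reader might infer that the MTD is compromised; DLTs are counted in Cycle 1 only. A reader might infer that Section 8.1 plainly pools changed patients; it can equally mean only the cohort assigned to the RP2D. It is Section 8.3.1 that takes them in.

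**Conclusion.** The point holds in two parts of different kinds.

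**Monitoring** is a design choice worth improving, not an error. From Cycle 3, a Day 1 change is followed by no scheduled CBC or chemistry until nominal Day 29 (+/-1), and a mid-cycle change by one draw in 28 days, against three for patients who start at that dose. This assumes no cycle delays and full 28-day windows. The number who will change is not given and is probably small.

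**The efficacy population** is wrong as written. Each patient who changes to the RP2D adds about 56 or more progression-free days at a lower dose to PFS and OS, and possibly an earlier response to ORR. This matters only if the expansion is conducted and someone changes to the RP2D; the analyses are descriptive and single-arm, but ORR is the expansion's primary endpoint.

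**What to change.** 1. **Table 2 footnote.** After a change to a higher dose, do CBC and chemistry with a symptom check on the day of change and on Days 8, 15 and 22 counted from the first dose at the new level; at minimum, Days 8 and 15. A Day 1 change then has three later draws in 28 days, as starters do. Cost: three added visits for a Day 1 change, since that day's draw already exists. A mid-cycle change needs three when d = 8, 15 or 22, because one draw coincides with the next cycle's Day 1, and four otherwise. If 1 to 4 patients change (an assumption), that is 1 x 3 = 3 to 4 x 4 = 16 visits. These are visits for patients otherwise dosing at home, with no invasive procedure.
2. **Sections 8.1 and 8.3.1.** Limit the RP2D efficacy population to patients whose first study dose was the RP2D, and summarise patients who changed to it separately. Cost: one sentence in each section and no new data.
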